1.3 Benefit/risk and ethical assessment

AZD0585 contains omega-3-acid as FFA and has an advantage of greater bioavailability over existing omega-3-acid EE alternatives because absorption of EEs is significantly dependent on stimulated intestinal hydrolysis (food-activated) for mucosal uptake (Ikeda et al 1995, Small 1991, El Boustani et al 1987, Hazra et al 1999, Lawson and Hughes 1988a, Lawson and Hughes 1988b, Beckermann et al 1990, Hansen et al 1998).

The meal-fat independency of the AZD0585 formulation is important for full treatment effects, as patients with hypertriglyceridemia are advised to restrict fat intake in order to reduce TG and the associated risk of pancreatitis or CVD events (NCEP 2002).

The total intake of EPA plus DHA in subjects will not exceed 3 g per day since the planned 4 g per day dose of AZD0585 contains approximately 75% EPA plus DHA. This dose level is in agreement with the 1997 FDA ruling of 3 g per day as Generally Recognized as Safe for this aggregate amount (FDA 1997). In a previous Phase I study with AZD0585 in healthy adult male Japanese subjects (D5881C00005), 4 g AZD0585 was safe and well tolerated following single- and multiple-dose and once-daily administration up to 14 days.

Additionally, AZD0585 4 g daily dose was safe and well tolerated for up to 3 years in subjects with Crohn's disease. Therefore it is considered that 52-week treatment period is applicable for this study.

The patients who are allocated to placebo group continue placebo treatment for 52 weeks. From ethical point of view, patients are allowed to use lipid lowering drugs and/or supplements except for omega-3-acid after Visit 8.

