2.3 Exploratory objectives

Exploratory Objective:	Outcome Measure:
To assess the time-course of efficacy-related parameters profile up to Week 52 and explore the efficacy characteristics of long-term use of AZD0585 2 g/4 g vs. placebo.	
 • Fasting serum lipid profile including TG, TC, HDL-C, LDL-C, VLDL-C and non-HDL-C. • Apo A-I, Apo A-II, Apo B, Apo B48, Apo C-II, Apo C-III, and Apo E. • Plasma fatty acids profile: EPA, DHA, AA, and EPA/AA ratio. • Small dense LDL and LDL-C/Apo B ratio. • Lp(a), RLP-C, PCSK9 and hs-CRP.

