3.8 Restrictions

Subjects will be instructed as follows for a specified period during the study:

1. Any new prescription medications or OTC preparations, supplements must be reported to study site staff during study period.
2. Continue existing therapy (if applicable) with antihypertensive agents at current dosages unless needed by the Investigators discretion during study period.
3. Fast overnight for at least 8 hours prior to each study visit, i.e., no food or beverage except water.
4. Withhold alcohol and refrain from intense exercise 24 hours prior to each study visit.
5. Do not donate blood for the duration of the study.
6. Statin dose should not be changed up to Visit 8 unless needed for safety reason at investigators discretion. Do not take lipid lowering drug except for statin up to Visit 8. Thereafter any lipid lowering drugs and/or supplements are allowed except for omega-3.
7. Subjects should not take investigational products on the morning of the study visit. Subjects bring study drug to each study visit and take investigational products just after the nearest meal after study procedure of the study visit.
8. Subjects must make every attempt to adhere to the dietary and physical activity changes and goals as discussed with the Investigator(s) during study period.
9. Women of child-bearing potential must immediately contact the Investigators if they suspect they might be pregnant and if they have changed, or plan to change their birth control method during study period.

The sponsor or designee should be contacted if the investigator is informed of any restriction violations. The sponsor will decide whether a subject with restriction violations will be allowed to continue study participation.

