5.1 Efficacy assessments

Blood samples will be taken at the times indicated in the Study Plan (see [Table 1](#)).

The samples are measured by SRL Medisearch Inc. The detailed procedure of sampling, handling and shipping is described in the standard operating procedure made by AstraZeneca.

The valuables for efficacy assessment are as follows;

- Fasting serum TG
- Fasting serum lipid profile: TC, LDL-C*, VLDL-C, HDL-C and non-HDL-C* (*direct method)
- Apolipoprotein: Apo A-I, Apo A-II, Apo B, Apo B48, Apo C-II, Apo C-III, and Apo E
- Plasma fatty acids profile: EPA, DHA, AA, and EPA/AA ratio
- Small dense LDL and LDL-C/Apo B ratio
- Lp(a), RLP-C, PCSK9 and hs-CRP

The plasma fatty acids profile (EPA, DHA, AA and EPA/AA ratio) data from Visit 4 or later and the serum TG values between Visit 4 and Visit 8 must not be disclosed to Investigators and patients until the study closure.

In addition, the plasma fatty acids profile data from Visit 4 or later and the serum TG values between Visit 4 and Visit 8 will be kept double-blinded until the interim database lock.

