5.2 Safety assessments

5.2.1 Laboratory safety assessments

Blood and urine samples for determination of clinical chemistry, haematology, coagulation, and urinalysis will be taken at the times indicated in the Study Plan (see [Table 1](#)).

Blood samples will be measured by SRL Medisearch Inc.

The detailed procedure of sampling, handling and shipping is described in the standard operating procedure made by AstraZeneca. In addition, the PI ensures that samples are labelled and shipped in accordance with the Laboratory Manual and the Biological Substance, Category B Regulations (materials containing or suspected to contain infectious substances

that do not meet Category A criteria), see Appendix C ‘International Airline Transportation Association (IATA) 6.2 Guidance Document’. Any samples identified as Infectious Category A materials are not shipped and no further samples will be taken from the subject unless agreed with AstraZeneca and appropriate labelling, shipment and containment provisions are approved.

Urinalysis will be performed at each study site by dipstick provided by SRL Medisearch Inc.

The following laboratory variables will be measured:

Table 2 Laboratory Safety Variables

Haematology/Haemostasis	Clinical Chemistry
B-Haemoglobin (Hb)	S-Creatinine
B-Leukocyte count	S-Bilirubin, total
B-Leukocyte differential count (absolute count)	S-Alkaline phosphatase (AP)
B-Platelet count	S-AST
B-Haematocrit	S-ALT
P-PT	S-Albumin
P-PTT	S-Potassium
Urinalysis	S-Calcium, total
U-Hb	S-Sodium
U-Protein/Albumin	S-Creatine kinase (CK)
U-Glucose	S-TSH
U-Pregnancy	B-HbA1c
	P-Glucose
	S-LDL-C
	S-Apo B

The Investigator should make an assessment of the available results with regard to clinically relevant abnormalities. The laboratory results should be signed and dated and retained at site as source data for laboratory variables. For information on how AEs based on laboratory tests should be recorded and reported, see Section 6.3.

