7.7 Concomitant and other treatments

Concomitant use of following medications or therapies is not allowed during study period.

- Fibrates, bile acid sequestrants, or niacin or its analogues (greater than 200 mg/day) or any drug for the purpose of lowering plasma cholesterol (except for statin) from the screening to Visit 8.
- Any EPA or DHA products, fish oil, or medications (e.g., Lotriga[®], Epadel[®]) or investigational drugs (e.g., AMR101) containing EPA or DHA during study period.
- Any supplement for the purpose of lowering plasma cholesterol (e.g., red rice yeast supplements) from the screening to Visit 8.
- Weight loss drugs (including OTC preparations) or programs during study period.
- Ketoconazole, erythromycin, clarithromycin, cyclosporine, itraconazole, or protease inhibitors during study period only for statin users.
- Any anticoagulants (e.g., warfarin, coumarin, heparin, Prazaxa[®] or enoxaparin) during study period.
- Oral or injected corticosteroids (other than intranasal or inhaled steroids used for allergies/asthma) during study period.
- Grapefruit juice >750 mL/day during study period only for statin users.
- Insulin during study period.

Concomitant use of tamoxifen, estrogens, progestins, and testosterone are allowed during study period without change of the dose regimen, if the treatment of those drugs is stable during screening.

Fixed dose statin can be used until Visit 8. No limit is set to use statin after Visit 8.

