8.5.6 Exploratory analysis

For efficacy and pharmacodynamic parameters, baseline and post-baseline measurements up to Week 52 will be summarized by treatment group. In addition, percent change from baseline to Week 52 Endpoint will also be presented. Week 52 Endpoint will be defined as last non-missing measurement after start of treatment.

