4.1.2.2 Endpoints

For fasting lipids (TG, TC, HDL-C, non-HDL-C, VLDL-C, and LDL-C), the Week 12 Endpoint is defined as an average of week 10 and week 12 measurements. For discontinued subjects, average of last non-missing two consecutive measurements up to week 12 is used as the week 12 Endpoint. If only a single measurement is available for a patient, it is used as the week 12 Endpoint.

For the other secondary efficacy parameters listed in section 3.2.2, if no measurement is available at Week 12, the last post-baseline single measurement up to Week 12 will be used if appropriate. Such cases will be presented as Week 12 (LOCF).

For any variables, last non-missing measurement up to Week 24/52 will be employed for Week 24/52(LOCF) evaluation if appropriate.

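### Lipid drugs added after Visit 8 can distort the long-term TG and LDL-C comparison with placebo, in either direction, and no planned analysis sets those values apart

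*Protocol*

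**What the plan says.** **Treatment rule.** Up to Visit 8 the statin dose is fixed and other lipid drugs are barred. After that, Protocol 7.7 states: "Fixed dose statin can be used until Visit 8. No limit is set to use statin after Visit 8". Protocol 3.8, item 6, adds: "Thereafter any lipid lowering drugs and/or supplements are allowed except for omega-3". Protocol 1.3 gives the reason, which is ethical and tied to 52 weeks on placebo: "patients are allowed to use lipid lowering drugs and/or supplements except for omega-3-acid after Visit 8".

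**What prescribers can see.** Protocol 5.1 masks the fatty acids from Visit 4 onward, and for TG says: "the serum TG values between Visit 4 and Visit 8 must not be disclosed to Investigators and patients until the study closure". It states no masking for TG after Visit 8 or for LDL-C at any visit. LDL-C is in the safety laboratory list (Protocol 5.2.1, Table 2), and the same section says: "The Investigator should make an assessment of the available results with regard to clinically relevant abnormalities".

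**The long-term question.** Protocol 2.3 sets an exploratory objective to "explore the efficacy characteristics of long-term use of AZD0585 2 g/4 g vs. placebo", with TG and LDL-C among the measures. Laboratory evaluations, LDL-C included, also belong to the primary 52-week safety objective.

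**The long-term analysis.** Protocol 8.5.6: "Week 52 Endpoint will be defined as last non-missing measurement after start of treatment". SAP 4.1.2.2, for any variable: "last non-missing measurement up to Week 24/52 will be employed for Week 24/52(LOCF) evaluation if appropriate". SAP 4.2.2.3 adds descriptive statistics by treatment and visit, and SAP 4.2.3.3 does the same for safety laboratory values. SAP 4.2.3.1 tabulates lipid-lowering drugs by group for the first 12 weeks, the first 24 weeks and the whole treatment period.

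**The concern.** The treatment rule is sensible; the gap is in the analysis. SAP Table 1, items 4 and 5, removes patients from the per-protocol set if they changed their statin or started another lipid drug, but only in the first 12 weeks. These events are restricted before Week 12 and freely allowed after it, yet only the early ones are handled. The drug-use tables show how many patients in each group took such drugs. They do not link that use to the patients' lipid values, and the statin subgroup in SAP Table 3 is defined by use at baseline.

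If add-ons follow high TG, more of them should go to placebo, and a TG effect that in fact persists could look as if it fades after Week 12. If AZD0585 raises LDL-C and statins follow, the rise could look as if it settles by itself. Those same statins also lower TG, so the TG difference could look larger than AZD0585 alone produced.

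**Working it through.** **1. The plan's own figure.** Protocol 8.2 gives power of at least 92% at Week 12 (SD 24, difference 12.5, 150 vs 75, two-sided 0.025).
- SE = 24 × √(1/75 + 1/150) = 3.39.
- 12.5/3.39 = 3.68, and 3.68 − 2.24 = 1.44, so power is 92.5% (92.2-92.3% with the t distribution).

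The figure reproduces and is not in question. No figure is given for any later week.

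**2. How add-ons move a group mean.** Let μ be the mean percent change without add-ons, r the share on an added drug, and e its relative lowering. Then

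observed change = 100 × [(1 + μ/100)(1 − r·e) − 1].

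For TG, take μ = −4, −15 and −21 for placebo, 2 g and 4 g. These are the medians that Protocol 1.1 reports for the earlier study in TG 200 to <500 mg/dL, used here as means. The values of r and e are assumptions.

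Worked case, 4 g, r = 30% on placebo and 10% on AZD0585, e = 20%:
- Placebo: 0.96 × 0.94 = 0.9024, or −9.8.
- 4 g: 0.79 × 0.98 = 0.7742, or −22.6.
- Difference: −12.8, against a true −17.

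| Add-on use, placebo / AZD0585 | e | 2 g (true −11) | 4 g (true −17) |
|---|---|---|---|
| 10% / 10% | 20%, 40% | −10.8, −10.6 | −16.7, −16.3 |
| 30% / 10% | 20%, 40% | −6.9, −2.9 | −12.8, −8.6 |
| 10% / 20% | 20%, 40% | −12.5, −14.0 | −18.2, −19.5 |

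Equal use hardly matters. More use on placebo shrinks the difference, and more use on AZD0585 widens it.

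For LDL-C with e = 30% and use of 10% on placebo vs 20% on AZD0585, a true +10 reads as 100 × (1.10 × 0.94 − 0.97) = +6.4. A true +5 reads as +1.7.

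**3. Add-on triggered by the same lipid (simulation).** Assumptions: 75 vs 150 patients; baseline TG median 240 mg/dL within 150-499; two-visit SD 24; true difference −12.5. A TG-driven add-on is possible from Week 16, because TG is masked through Visit 8. The chance of an add-on is 5-20% at each visit at or above the trigger, and the add-on lowers TG by 20-40%.

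| TG trigger | Uptake by Week 52, placebo vs AZD0585 | Loss (points) |
|---|---|---|
| ≥300 mg/dL | 11-32% vs 7-22% | 1.0 to 5.0 |
| ≥200 mg/dL | 26-67% vs 21-57% | 1.4 to 6.9 |

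For LDL-C (trigger ≥140 mg/dL, drug effect 20-30%), a true +10 loses 1.4 to 4.6 points and a true +5 loses 0.6 to 2.3. A true 0 stays within 0.2 of 0.

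**4. Add-on triggered by the other lipid.** Add to the TG model a statin trigger at LDL-C ≥140 mg/dL, a true LDL-C rise of 10 points, and a statin that lowers LDL-C by 30% and TG by 15-25%.
- LDL-C trigger only: the TG difference of −12.5 reads as −12.8 to −14.0, a widening of 0.3 to 1.5 points.
- Both triggers (TG ≥300, 30% add-on effect): a loss of 0.6 to 2.9 points.

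**5. Does setting post-add-on values to missing help?** With both triggers, a repeated-measures model gave −12.1 to −13.0 against a true −12.5. Its SD was about 4.2 to 5.2. With the TG trigger alone at ≥300, the SE was 3.9-4.4, against 3.5-4.1 for all values.

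**The case against.** The case for leaving the plan alone is substantial.

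- **Exploratory and descriptive.** Everything beyond the primary endpoint is read descriptively. No placebo difference, interval, model or test is planned after Week 12, so no planned estimate is wrong. This stands, and it limits the point to interpretation.
- **The summaries answer a valid question.** They compare two strategies that include free lipid care. This stands, and they should stay. The stated objective, however, is AZD0585 against placebo.
- **Partly visible already.** Readers get drug use by group, and lipid summaries at Weeks 16 and 20, before much add-on use can build up. This helps a reader notice an imbalance, but not see its effect on TG or LDL-C.
- **Size not anchored.** The upper losses need up to 67% of placebo patients to start a drug. About half or more of the patients are to be statin users, and inclusion criterion 4 requires an optimal or maximally tolerated dose, so a uniform 20-30% add-on effect on LDL-C is doubtful. With the ≥300 trigger, most losses are no larger than about one standard error (3.5-4.1). This stands.
- **The remedy trades bias for variance.** With both triggers, the model's root-mean-square error was 4.2-5.1, against 4.0-4.5 for all values. It therefore cannot replace the planned tables.

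A reader might infer that the planned tables always understate the AZD0585 effect. They need not: statins given for LDL-C can widen the TG difference. Nor do the documents show that LDL-C will rise here. Protocol 1.1 reports a rise in the earlier study at TG 500 to <2000 mg/dL and gives no LDL-C result for the one at 200 to <500. The confirmatory Week 12 result is not in doubt either, because the free period starts after it.

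**Conclusion.** The gap is real and minor: a cheap improvement that the sponsor could make. The long-term lipid summaries mix the effect of AZD0585 with that of drugs that may have been given because of those lipids, and nothing planned separates the two.

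Neither direction nor size can be fixed from the documents. The scenarios run from a slight widening to a loss of several points on a true TG difference of −12.5. All of them rest on assumed uptake, thresholds and drug effects, and on investigators acting on TG or LDL-C values that no document says are withheld. The LDL-C concern is conditional on a true rise in this population. Confidence is medium.

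**What to change.** 1. Keep the planned tables and add a footnote that values after Week 12 include lipid-lowering drugs added after Visit 8.
2. Add to SAP 4.2.2.3 one supportive analysis each for TG and LDL-C on the FAS. Take percent change at all post-baseline visits to Week 52, and set values after the first start, switch or dose increase of a lipid-lowering drug to missing. Fit an MMRM with treatment, visit, treatment-by-visit, baseline statin use and baseline value, plus TG strata for LDL-C as in SAP 4.2.2.2.
3. Preferably let the other lipid's recorded values inform the missing data, for example by multiple imputation. A TG value may be set to missing because of an LDL-C result, and a model with TG alone does not condition on that.
4. Report the difference to placebo with 95% CI and the number still contributing at Weeks 24 and 52, labelled supportive and descriptive, beside the all-values tables.

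**Cost.** SAP text and two models, using lipid and medication records already collected; nothing changes for patients or sites. MMRM, MAR and MI are already in the SAP abbreviation list, though no analysis uses them. The price is reliance on missing at random and a TG standard error of about 4 to 5 points, against about 3.5 to 4 for all values.

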7.8 Post Study Access to Study Treatment (Not Applicable)

8. STATISTICAL ANALYSES BY ASTRAZENECA

8.1 Statistical considerations

- All personnel involved with the analysis of the study will remain blinded until database lock and protocol violators identified.
- Analyses will be performed by AstraZeneca or its representatives.

8.2 Sample size estimate

A common standard deviation of 24% is assumed for primary efficacy variable (percent change from baseline to Week 12 Endpoint in serum TG). One hundred and fifty patients in both of AZD0585 2 g and AZD0585 4 g and 75 patients in placebo will ensure the power for detecting 12.5% difference of AZD0585 each dose vs. placebo to be at least 92%, based on t-test with two-sided significance level of $0.05/2 = 0.025$.

In the above calculation, it was assumed that a total of 375 patients are to be randomised to placebo, AZD0585 2 g, AZD0585 4 g with ratio of 1:2:2 and that proportion of randomised patients not contributing primary analysis at Week 12 Endpoint is negligible.

In addition, the above sample size is expected to be sufficient to provide long term safety data of more than 100 Japanese patients treated by AZD0585 2 g or by AZD0585 4 g for 1 year.

8.3 Definitions of analysis sets

Randomised set: all patients who received randomisation number.

8.3.1 Efficacy analysis set

Full Analysis Set (FAS): all randomised set who had both any baseline and any post-baseline efficacy measurements. Patients will be analyzed according to their randomised treatment. FAS will be considered primary analysis set used for all efficacy evaluation.

Per Protocol Set (PPS): all patients in FAS who completed the first 12-week treatment period without any significant protocol deviations affecting primary efficacy evaluations. All criteria to exclude patients from the PPS will be made prior to the unblinding of the study. Patients will be analyzed according to their randomised treatment. Analyses on PPS will be of supportive purpose and limited to primary and important secondary efficacy variables.

8.3.2 Safety analysis set

Safety set: all patients who took at least one dose of double-blind study medication. Patients will be analyzed according to actual medication received.

8.4 Outcome measures for analyses

8.4.1 Primary efficacy variable

Primary efficacy variable is percent change from baseline to the Week 12 Endpoint in serum TG.

8.4.2 Secondary efficacy variables

- Percent change from baseline to the Week 12 Endpoint in TC
- Percent change from baseline to the Week 12 Endpoint in HDL-C
- Percent change from baseline to the Week 12 Endpoint in non-HDL-C
- Percent change from baseline to the Week 12 Endpoint in LDL-C
- Percent change from baseline to the Week 12 Endpoint in VLDL-C
- Percent change from baseline to Week 12 in Apo A-I
- Percent change from baseline to Week 12 in Apo A-II
- Percent change from baseline to Week 12 in Apo B
- Percent change from baseline to Week 12 in Apo B48
- Percent change from baseline to Week 12 in Apo C-II
- Percent change from baseline to Week 12 in Apo C-III
- Percent change from baseline to Week 12 in Apo E
- Percent change from baseline to Week 12 in EPA
- Percent change from baseline to Week 12 in DHA
- Percent change from baseline to Week 12 in AA
- Percent change from baseline to Week 12 in EPA/AA ratio
- Percent change from baseline to Week 12 in Small dense LDL
- Percent change from baseline to Week 12 in LDL-C/Apo B ratio
- Percent change from baseline to Week 12 in Lp(a)
- Percent change from baseline to Week 12 in RLP-C
- Percent change from baseline to Week 12 in PCSK9
- Percent change from baseline to Week 12 in hs-CRP

8.5 Methods for statistical analyses

8.5.1 Analysis of the primary variable (s)

Primary analyses will be carried out by analysis of covariance (ANCOVA) model including percent change from baseline in TG at Week 12 Endpoint as a response variable, treatment and baseline statin use as factors and baseline TG as a covariate. The primary analysis will be carried out on FAS.

Least square means and 95%CI for each treatment as well as treatment difference to placebo will be provided from the model. P-values will be provided for comparison of AZD0585 each dose vs. placebo.

As a sensitivity analysis, log-transformed TG at Week 12 Endpoint will also be analyzed by ANCOVA model including treatment and baseline statin use as factors and log-transformed baseline TG as a covariate. Least square means and 95%CI for treatment difference to placebo will be back transformed and presented as relative treatment difference to placebo in percent change from baseline of TG.

Definition of Endpoint and baseline & missing values

Baseline is defined as average of Week -4, -2 and 0.

Week 12 Endpoint is defined as an average of measurements Week 10 and Week 12.

If patients drop out before Week 12, average of the last two consecutive post-treatment values will be used for Week 12 Endpoint evaluation. If only one post-baseline measurement is available, it will be employed for Endpoint evaluation. Data obtained after Week 12 visit will not be used for evaluation of Week 12 Endpoint.

It is assumed that most patients will complete 12-week treatment without major deviations and the above approach would provide approximately unbiased estimates for treatment effects. However, further sensitivity checks may be planned and documented in Statistical Analysis Plan.

Confirmatory Hypothesis Family & Multiplicity

The primary objective of this study is to demonstrate the efficacy of AZD0585 2 g and 4 g when compared with placebo using the percent change from baseline in TG to Week 12 as a primary efficacy variable. In order to protect family wise error rate to be 5%, superiority of AZD0585 2 g vs. placebo and superiority of AZD0585 4 g vs. placebo will be tested based on Hochberg procedure using two-sided significance level of 0.05. If a p-value for each hypothesis is less than $0.05/2 = 0.025$, the corresponding hypothesis claimed to be demonstrated. If both p-values are less than 0.05, then the both hypotheses are claimed to be demonstrated.

All analyses other than analysis of the primary efficacy endpoint will be interpreted descriptively. Consequently, no adjustments for multiplicity will be necessary for such analyses. Ninety-five percent confidence intervals will be calculated, where appropriate, as measures of study precision. P-values may be calculated but are to be regarded as descriptive.

